2. OBJECTIVE

2.1 Primary Objective:

To examine differences in dose reductions, dose delays and early stoppage for chemotherapy and the total combined number of moderate and severe chemotherapy-associated toxicities between intervention group and waitlist controls.

2.2 Secondary Objectives:

2.2.1 Examine specific inflammatory markers (CRP, IL-6, TNF- α receptor II [TNF-RII]) in relation to baseline MM and FM and examine differences in changes in inflammatory markers between intervention group and waitlist controls.

2.2.2 Examine the impact of intervention versus control and RT-induced body composition changes on the pharmacokinetics [PK] of 5-FU and oxaliplatin between baseline and 4 months of RT.

2.3 d3 Creatine Objectives:

2.3.1 Test whether resistance training during chemotherapy (FORCE intervention group v. control) increases d3 creatine muscle mass at 6 months.

2.3.2 Evaluate the association of d3 creatine muscle mass with changes in functional status and strength during chemotherapy.

2.3.3 Evaluate the association of d3 creatine muscle mass with chemotherapy toxicity and relative dose intensity.

2.3.4 Evaluate the association of d3 creatine muscle mass with cancer-related biomarkers, including inflammation, CEA levels and cardiometabolic risk factors.

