Details of each patient's health history, including medical imaging, comorbidities and colon cancer diagnosis and treatment details will be extracted from the EMR. In addition, laboratory and clinical data about the colon cancer tumor marker Carcinoembryonic Antigen (CEA) and cardiometabolic risk factors blood glucose, lipids, blood pressure and medication usage conditions will be extracted from the EMR. See Appendix 13.2.1. A researcher will record all relevant medical variables in an online REDCap form. In addition, CT scans will be obtained from the participant's medical record. KP scans will be stripped of PHI and analyzed at DOR. Penn State and DFCI scans will be stripped of PHI and transmitted directly to DOR via SFT. CT scan closest to the date of diagnosis but before chemotherapy will be colored using TomoVision sliceOmatic software to determine body composition, including muscle attenuation.

4.10 Body composition and body size:

At the baseline visit and at the follow-up visit, a DXA scan to assess body composition will be performed (see Appendix 13.8.2). All DXA scans will be performed in the total body scanning mode. A third scan will take place after 4 months for the subset of people participating in the PK study to correspond to timing of the 2nd PK blood draws.

At the baseline visit and at the follow-up visit, d3-creatine dilution will be used to accurately assess total body skeletal muscle mass (see Appendix 13.8.3).

Height and weight will be assessed using a scale mounted stadiometer and digital scale (or per institutional clinic standards) to the nearest 0.1 cm and 0.1 kg. Waist circumference and hip

circumferences will be measured at standardized landmark with participants dressed in light indoor clothing without shoes. Height will be assessed at baseline only. A researcher will record anthropometric measurements in an online REDCap form. See Appendix 13.8.1.

Because of COVID-19, if a participant doesn't feel comfortable with study staff touching him/her for waist or hip circumference measures, the study staff can teach the participant how to self-measure while observing and recording results in REDCap.

4.11 Dose reductions/delays and early discontinuation of treatment:

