Pharmacokinetics: As 5-FU is known to undergo nonlinear disposition, compartmental modeling will be conducted using nonlinear mixed effects analysis with NONMEM (Icon Development Solutions, Hanover MD). NONMEM allows for simultaneous estimation of fixed-effects values (e.g. CL and V) and random-effects values (e.g. inter-individual, inter-occasional, and residual unexplained variability). Previous models of 5-FU and oxaliplatin²⁸ have been reported and will serve as a basis for development of the structural model. The final structural (e.g. 1- vs. 2-compartment) and error models (e.g. additive or proportional) will be chosen based on minimization of the objective function value (OFV, $-2 \log$ likelihood) and evaluation of diagnostic plots generated in R. During the covariate selection process, various measures of body composition (e.g. MM, MM/FM ratio) will be compared to identify the contribution of these parameters to PK variability in colon cancer patients. Pre- and post-intervention PK parameters (e.g. CL, V) will be compared using a paired t-test.

9.3.3 d3 creatine endpoints:

We will first assess the distribution of the baseline covariates by FORCE randomization arm. Most outcomes will be treated as continuous variables and we will fit linear regression models (e.g., for the continuous outcomes such as change in d3 creatine muscle mass, SPPB and SF-36 score, grip strength, relative dose intensity, and values of inflammatory markers, CEA and cardiometabolic risk factors). We will assess departures from regression model assumptions primarily by diagnostic plots of residuals, with attention to detection of non-constant variance of errors and detection of outliers that may indicate the need for a variance stabilizing transformation of the dependent variable. In secondary analyses, when considering outcomes dichotomously, we will fit logistic regression models (e.g., for abnormal CEA values).

Aim 1 is a randomized comparison of the FORCE resistance training intervention to the waitlist control. Analyses in Aims 2-4, however, are subject to confounding. Our *a priori*

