set of potential confounders for cross-sectional analyses at baseline includes age, sex, body mass index or weight, race/ethnicity and tumor stage. For longitudinal analyses, potential confounders also include chemotherapy type, intervention assignment and time from surgery and/or chemotherapy start to assessment. We will include those covariates resulting in a 10% or more change in the d3 creatine muscle mass regression coefficient. The change-in-estimate approach to confounder selection performs well with regard to power, bias, mean squared error and confidence interval coverage.

9.3.4 Power:

Given previous exercise studies in cancer patients, we assume approximately 10% drop out with no follow-up DXA and blood draw for biomarker assessment. We expect chemotoxicity metrics (RDI, # toxicities) to be assessed on the full sample. We have sufficient power (.80) to detect a between arm difference in means of at least .42 standard deviation (s.d.) units (two-sided t-test, $\alpha=.05$) in Aim 1 analyses of chemotoxicity. With an expected RDI s.d. of 17.3⁴⁵, the minimum detectable difference in mean RDI is 7.3%, which is clinically meaningful and similar to effects found with a study of exercise among breast cancer patients receiving adjuvant chemotherapy⁴⁵. With the expected loss to follow-up and reduced sample size of 81 per group, the minimum detectable between arm difference in mean change is .44 units, which is considered in the “small” to “medium” range in effect size using the terminology and classification of Cohen. Relevant to Aim 4, on pharmacokinetics, a sample size of 30 subjects will provide sufficient power (.80) to detect a mean change of at least 0.5 s.d. units (two-sided t-test, $\alpha=.05$). Given previous data²⁶, the minimum detectable change in clearance of oxaliplatin or 5-FU due to RT is 15%.

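### Adjusting d3 muscle mass for BMI or weight, with fat mass left out, can make muscle look protective in the biomarker models when it has no effect

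*Protocol*

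**What the plan says.** Protocol section 2.3.4 sets the objective: "Evaluate the association of d3 creatine muscle mass with cancer-related biomarkers, including inflammation, CEA levels and cardiometabolic risk factors". Section 9.3.3 says that for continuous outcomes "we will fit linear regression models", and it concedes that "Analyses in Aims 2-4, however, are subject to confounding".

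The a priori "set of potential confounders for cross-sectional analyses at baseline includes age, sex, body mass index or weight, race/ethnicity and tumor stage". The longitudinal models extend that list: "For longitudinal analyses, potential confounders also include chemotherapy type, intervention assignment and time from surgery and/or chemotherapy start to assessment". Selection from the list follows a change-in-estimate rule: "We will include those covariates resulting in a 10% or more change in the d3 creatine muscle mass regression coefficient".

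Fat mass is in neither list, and height appears only inside BMI. The SAP as supplied does not mention d3 creatine, so it does not settle the choice.

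Fat mass is nevertheless in the study. Secondary objective 2.2.1 examines inflammatory markers "in relation to baseline MM and FM and examine differences in changes in inflammatory markers". Section 4.10 says "At the baseline visit and at the follow-up visit, a DXA scan to assess body composition will be performed", and d3-creatine dilution is scheduled at the same two visits. Section 4.10 also says that height is taken at baseline only.

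**The concern.** Weight is the sum of muscle, fat and other tissue, so it includes the exposure. Comparing two patients of equal weight, one with more muscle, means comparing a patient who has less fat or less other tissue. The muscle coefficient then describes muscle exchanged for fat. It is not the association of muscle with the marker that the objective names.

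If fat raises CRP, glucose or lipids, a muscle coefficient at fixed weight will tend to be negative even when muscle is irrelevant. A report that more muscle goes with less inflammation could then not be told apart from less fat going with less inflammation. Because the plan leaves the size variable open, the size and significance of the coefficient, and in some cases its sign, depend on a choice not yet made.

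**Working it through.** **1. The plan's own figures.** Section 9.3.4 gives no power or precision figure for the d3 association models. Its nearest figures reproduce: (1.960 + 0.842) × √(2/90) = 0.418, against 0.42 stated, and (1.960 + 0.842) × √(2/81) = 0.440, against 0.44. They matter here only for sample size: 180 planned, and 2 × 81 = 162 after the assumed 10% loss of DXA and blood.

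**2. Algebra.** Write M for muscle, F for fat, R for other tissue and W = M + F + R. Let the marker be bM·M + bF·F + error. Substituting F = W − M − R gives

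bM·M + bF·F = (bM − bF)·M + bF·W − bF·R.

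With M and W in the model and R left out, the coefficient on M is bM − bF·(1 + ρ), where ρ is the slope of R on M at fixed weight. In general the coefficient is bM + λ·bF, where λ is the slope of fat on muscle given sex and the size variable. For weight, λ = −(1 + ρ).

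**3. Values of λ.** The documents supply none of the inputs, so these are assumptions. Within-sex SDs are 3-5 kg for muscle, 6-12 kg for fat and 3.5 kg for other lean tissue. Correlations of muscle are 0 to 0.5 with fat, 0.2 to 0.6 with height and 0.5 to 0.8 with other lean tissue. Ten combinations were computed.

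| Size term (with sex) | λ, base case | λ, range |
|---|---|---|
| none | +0.67 | 0 to +1.12 |
| weight | −1.12 | −0.95 to −1.52 |
| BMI | −0.34 | −0.11 to −0.57 |

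BMI is milder because, without a height term, more muscle at the same BMI partly means a taller person. Adding height to BMI removes that relief: λ returns to −0.99 in the base case.

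**4. Expected muscle coefficient, base case, bF = 0.03 log units per kg (assumed).**

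| True bM | no size term | weight | BMI | fat mass |
|---|---|---|---|---|
| −0.03 | −0.010 | −0.064 | −0.040 | −0.030 |
| 0 | +0.020 | −0.034 | −0.010 | 0.000 |
| +0.015 | +0.035 | −0.019 | +0.005 | +0.015 |

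For example, at bM = 0 with weight, −1.12 × 0.03 = −0.034. Weight and BMI have opposite expected signs only when bM/bF lies between 0.34 and 1.12, that is, when muscle itself raises the marker.

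**5. The 10% rule.** At bM = 0, adding weight moves the coefficient from +0.020 to −0.034, a change of 0.054 against a threshold of 0.1 × 0.020 = 0.002. BMI moves it by 0.030. In 2,000 simulated samples of 180 per setting, the rule kept either size term in 99-100% of samples. It reads the exchange of muscle for fat as confounding.

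**6. False protective findings.** These are significant negative muscle coefficients at two-sided 0.05 when bM = 0, so the nominal rate is 2.5%. Residual SD is 1.0 (assumed).

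| Setting | weight | BMI | with fat mass |
|---|---|---|---|
| n = 180, bF = 0.03, base case | 25% | 6% | 3% (fat mass) |
| n = 162, bF = 0.02-0.05, several assumed covariance sets, muscle-fat correlation 0.1-0.3 | 13-79% | 5-30% | about 2.5% (fat mass + height) |

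Dropping the size term is no remedy. In the n = 180 base case it gives a significant positive coefficient in 17% of samples, because larger people tend to have more of both tissues.

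**The case against.** **Estimand.** The objective asks for an association, and muscle at a given body size is a legitimate question. Section 1.5 itself points to patients of equal body surface area who differ widely in muscle. This stands as far as it goes: a weight-adjusted model is not invalid. But the plan never labels its result as muscle in place of fat, and it does not choose between two size terms that carry very different amounts of the fat effect.

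**Conditional adjustment.** The listed covariates are only candidates. That is true, but step 5 shows that the rule would almost always retain the size term.

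**Assumed magnitude.** Every rate above rests on assumed inputs, and the simulated marker is driven by fat, so a model containing fat is bound to do well. This stands. The rates show what follows if fat raises the marker. They do not estimate the bias in this trial, and nothing here shows a fat effect on CEA.

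**Handled elsewhere.** Objective 2.2.1 will report baseline associations of fat mass with inflammatory markers, and section 9.3.3 admits confounding. Both limit misreading, but neither changes the d3 models.

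**Stronger readings.** A reader might infer that the sign of the muscle coefficient turns on whether BMI or weight is picked. The documents do not support that as a general statement. With muscle null or protective, both expected coefficients are negative, and in step 4 they differ in size by a factor of about 1.6 (0.064/0.040) to 3.3 (0.0336/0.0102). Estimated signs can still disagree by chance: in 23% of samples of 180 at bM = 0 and 2% at bM = −0.03. A reader might also infer that any protective result must be a fat effect. That goes too far, above all for BMI, where the base-case rate is 6%.

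**Conclusion.** The concern holds for the cross-sectional biomarker models of objective 2.3.4. The only size covariate offered is BMI or weight, the choice is open, and measured fat mass is left out. The algebra for weight needs no numerical assumption beyond a linear model: the muscle coefficient carries roughly minus the fat effect. BMI carries about 0.1 to 0.6 of it under the assumed body compositions. If fat raises the marker by .02-.05 log units per kg and muscle does nothing, the false protective rate is about 13-79% with weight and 5-30% with BMI, against the nominal 2.5% once fat mass and height are in the model.

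The size and significance of the coefficient depend on the unspecified adjustment. Its sign does so in some cases, chiefly between no size term and either size term, or when muscle itself raises the marker. The argument covers cross-sectional models. Models of change in muscle given baseline size were not examined, and the identity in step 2 does not carry over to them directly. The primary endpoints and the randomised d3 comparison (2.3.1) are untouched. This is a cheap improvement to a set of observational analyses.

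**What to change.** In section 9.3.3, for the cross-sectional biomarker models of 2.3.4, replace the open choice between BMI and weight with a fixed model: d3 muscle mass, DXA fat mass from the corresponding assessment, and baseline height. Height must come from baseline because it is not measured again. Keep these terms outside the 10% rule, which can still govern the remaining candidates.

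If a weight- or BMI-adjusted model is also reported, show it as a sensitivity analysis and label it. The weight-adjusted coefficient should be described as muscle in place of fat at the same weight.

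The cost is a line or two of text and no new measurement. Participants without a DXA at the assessment drop out of these models. At follow-up that loss largely overlaps the roughly 10% whom section 9.3.4 already assumes to lack both DXA and blood.

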3. INTERVENTION

3.1 Rationale for home-based resistance training:

Resistance training increases muscle mass through hypertrophy of muscle cells³⁵. A recent meta-analysis identified 11 resistance training intervention trials conducted within individuals with cancer³⁶. In the six trials that evaluated intervention effects on MM, the weighted mean effect size was a statistically significant increase of 1.07 kg MM ($p < 0.0001$). The interventions ranged from 12 to 52 weeks in length, 2 to 4 exercise sessions per week, with intensity described by percent of maximal (25-80% of 1 repetition maximum (RM)), or according to rate of increase (gradually, with the smallest available increment of resistance). The meta-analysis did not see further benefit of more than 2 sessions per week, and low to moderate intensity netted as much benefit as high intensity programs. Both women ($n=818$) and men ($n=313$) were represented in these trials and the beneficial effects were observed in both genders. Finally, more pertinent to the proposed work, a post-hoc analysis of data from a large resistance training trial in breast cancer survivors conducted by Co-PI [name] indicates that appendicular skeletal mass was better maintained in the intervention group who did twice weekly strength training when compared to usual care controls³⁷. There have been fewer home-based resistance training studies than supervised or facility-based studies among cancer survivors. However, a systematic review on home based resistance training specifically for older adults demonstrated that home based resistance training programs can improve strength and functional ability³⁸. Additionally, home based resistance exercise is generally well tolerated by cancer survivors and

has demonstrated benefits in physical function, strength and/or quality of life in patients with prostate cancer^{39,40} and breast cancer⁴¹⁻⁴³.

3.2 Target population:

All newly diagnosed, Stage II and III, colon cancer patients within the first weeks of chemotherapy will be selected for participation in the study. Recruitment strategies will vary at each site (KPNC, PSCI, and DFCI).

3.3 Key inclusion criteria:

- Men and women ≥ 18 years
- Newly diagnosed with histologically confirmed stage II-III colon cancer
- Completed curative-intent surgical resection
- Currently prescribed one of the following adjuvant chemotherapy regimens: (IV 5-fluorouracil [5-FU] / leucovorin [LV], capecitabine, FOLFOX [5-FU, LV, oxaliplatin], CAPOX [capecitabine and oxaliplatin]
 - Patients must have started chemotherapy or plan to start, with planned receipt of the first exercise visit **by the third infusion visit**.
 - Patients receiving FOLFOX chemotherapy are eligible to enroll in the pharmacokinetics sub-study (see section 3.10).
- No planned major surgery anticipated in the intervention period
- Sufficient time to heal from any major surgery to start of intervention, including colostomy reversal (port-a-cath removal excluded)
- Creatinine value < 2 mg/dL
- Approval by either oncologist or surgeon to participate in trial
- Readiness (as determined by the Physical Activity Readiness Questionnaire (PAR-Q) – see Appendix 13.2.2)
 - If there are any indications that home based exercise would be unsafe based on PAR-Q the patient will not be enrolled until confirmation from the patient's treating provider is received via email and/or phone that they are safe to exercise. Provider does not need to be contacted if patient answers 'yes' to 'Is your doctor currently prescribing any medication for your blood pressure or for a heart condition?'
- Ability to understand and the willingness to sign a written informed consent document in English
- Willingness to be randomized

3.4 Exclusion criteria:

- Concurrent actively treated other cancer (except non-melanoma skin cancer, in situ cervical cancer or localized prostate cancer treated with surveillance only)
- Patients with untreated hypertension (> 180 mm Hg systolic or > 100 mm Hg diastolic) appearing in the patient's medical record in the two weeks prior to screening will not be enrolled until confirmation from the patient's treating provider is received via email and/or phone that they are safe to exercise.
- Presence of metastatic disease
- Current strength training ≥ 2 x week for the past 3 or more months
- Patients enrolled in other clinical trials of weight loss, physical activity or dietary interventions are ineligible.

3.5 Inclusion of women and minorities:

We seek to recruit 180 participants with a diagnosis of colon cancer. We will not exclude any participants due to their race and ethnicity. All races are accepted. The distribution of

participants by race and ethnicity is expected to mirror that of the institution's colon cancer patient population.

3.6 Patient recruitment, registration and randomization requirements:

Prior to initiating recruitment, each study site will obtain separate IRB approval from their respective institutions. Each collaborating site is under their own IRB's purview. Patient recruitment will be specific to each site. At all sites, participants must have the approval of a treating provider in order to participate in the study.

Kaiser Permanente Northern California recruitment:

At KPNC, potentially eligible study participants will be identified using the Electronic Medical Record (EMR) and a pathology database which is updated daily with newly diagnosed cancer cases. Additionally, oncology providers will be made aware of the study and will be asked for patient referrals at each Kaiser facility. Through the EMR, each stage II-III colon cancer patient will be identified close to the time of diagnosis and passively followed through surgery. After confirmation of chemotherapy prescription at the time of first oncology visit, the oncologist will be emailed through our secure internal email system to request approval for study participation for their patient and permission to contact the patient (see Appendix 13.1.1). Once permission is received from the oncologist, we will contact the patient through our secure internal email system and USPS mail, and then by phone to invite them to the study and to screen for eligibility using the above criteria. Contact information (i.e., email, address, phone number) will be identified using the EMR. The MD recruitment email, the participant recruitment email/letter and the recruitment phone script can be found in the Appendix 13.1.

Dana-Farber Cancer Institute recruitment:

Patients will be recruited from the patient populations of the Gastrointestinal Cancer Center clinics at Dana-Farber Cancer Institute. We will utilize multiple active recruitment techniques to maximize participation and generalizability. We will use the following strategies to identify potential participants

- Review of clinic schedules and patient lists for medical oncologists at Dana-Farber to identify patients with Stage II-III colon cancer. HIPAA waiver will be obtained to review these patient lists.
- Education of oncology providers of availability of protocol to encourage oncology providers to identify patients for study staff.
- Tumor registries at Dana-Farber
- Advertisements in patient areas

For potential participants identified through patient lists, we will contact provider and request permission to contact their patients. Providers will be asked to indicate any patients who should not be approached regarding participation in this study. Patients whose provider either provided permission to contact or who did not respond to email request will be assumed to be appropriate to approach. Once potential participants are identified, they will be contacted during next clinic visit or through mailing (see Appendix 13.1.2).

Interested subjects at Dana-Farber identified through these recruitment strategies will be screened by study staff either in person or by phone initially and if potentially eligible, he or she will schedule a visit with a member of the study staff to review the protocol and sign informed consent. All participants must have the approval of a treating provider in order to participate in the study.

Penn State Cancer Institute recruitment:

At PCSI, we will recruit by having a staff person review the EMR to identify potentially eligible patients. The study staff will approach the treating oncologist for permission to contact potentially eligible patients. Upon written (email) confirmation of permission to contact, the research coordinator will contact him/her by phone. During this phone call, the study will be briefly described, and study staff will ask if the patient would be willing to allow study staff to visit in person at the next clinic visit. Brief screening will also take place during this initial phone call (see Appendix 13.2). Patients found to be provisionally eligible based on this initial screening who are interested in hearing more will be visited in person by a study staff person to further discuss the trial and to proceed with the consent process if appropriate. Prior to starting recruitment, Co-PI [name] will visit the GI research conference and the GI tumor board meetings to describe the trial to the medical oncologists who treat colon cancer at PSCI and answer any questions they may have.

